Medical and Psychiatric Evaluation: Once written informed consent has been obtained, the diagnosis will be confirmed by a Structured Clinical Interview for DSM IV (SCID). A detailed medical and psychiatric history, physical examination (including vital signs, height, and weight), an electrocardiogram, and laboratory assessments (standard screening blood tests: CBC with differential and platelet count, electrolytes, creatinine, BUN, liver enzymes, T4, calcium, phosphate, TSH, and magnesium levels) will be performed. In addition, a full lipid profile, fasting glucose and insulin levels will be obtained. A pregnancy test will be done in all premenopausal women. A routine urinalysis and drug screen will be done as part of the screening process.

Subjects will be administered the PANSS and motor side effects scales (AIMS, Barnes akathisia scale, Simpson Angus scale). IQ will be measured at screening using the Wechsler Test of Adult Reading (WTAR). Subjects will also be asked to provide an informant who can be contacted to collect clinical and safety information relevant to the outcome measures on each visit. This could be a clinician or a family member/friend who sees the patient at least on a weekly basis.

Study Design: In this 2 period cross over design, subjects will be randomized in a 1:1 ratio to receive either: **Order 1**: CBD (Period 1) followed by placebo (Period 2) or **Order 2**: Placebo (Period 1) followed by CBD (Period 2) under double-blind conditions. The 2 study periods will be separated by a washout of at least 2 weeks. During each period subjects will receive study medications (CBD [total 800mg/day] or placebo) for a period of 4 weeks. This dose is within the dose range of doses that have been shown to be effective and safe. Randomization to the order of medication assignment will be stratified by baseline PANSS scores.

Study Visits:

Subjects will have the following visits during each period except for Visit I (screening), which will occur only at the beginning of their participation in the study:

Visit I: Screening (At least two visits: Visit Ia and Visit Ib.)

Visit II: Baseline: Will initiate treatment with study drug following baseline assessments.

(Visits III, IV, V: Weekly clinical evaluation and study medication refill)

Visit III: (Week 1)

Visit IV: (Week 2)

Visit V: (Week 3)

Visit VI: (Week 4): End of treatment period visit

Visit VII: Safety Follow up at week 5.

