DSMB: A Data Safety Monitoring Board is being assembled for this study. Unblinded safety data will be provided to the committee for monitoring purposes, in a meeting that will be held approximately every 6 months. DSMB reports will be provided to the HIC.

11. Statistical Considerations:

General Strategy:

All outcomes will be summarized descriptively and assessed for normality prior to analysis using normal probability plots and Kolmogorov test statistics. Transformations or nonparametric analyses will be performed as necessary. All tests will be two-sided and considered statistically significant at alpha=.05. Post-hoc comparisons will be performed as appropriate and significance levels for secondary analyses will be adjusted for multiple tests using the Bonferroni correction. All analyses will be performed using SAS, version 9.3 (SAS Institute Inc., Cary, NC).

Linear mixed models will be used assess symptom improvement as measured by the PANSS (primary hypothesis) and CGI. In these models group (CBD vs. placebo) and time (see study time points) will be modeled as within-subjects factor. Oder effects will also be tested. Least squares means and standard errors will be calculated in the mixed model and plotted to interpret significant effect. A significant group by time interaction explained by reduced symptoms over time due to CBD treatment will be supportive of our hypothesis. In the above models, the best fitting variance-covariance structure will be selected based on information criteria. The mixed effects approach is advantageous in that it is unaffected by randomly missing data and allows greater flexibility in modeling the correlation structure of repeated measures data [31]. Similar mixed models as described above will be employed to evaluate secondary outcomes (e.g., PAOFI, EEG parameters).

Power Analysis:

We will recruit 36 subjects and randomly assign 18 to receive either CBD followed by placebo (order 1) or placebo followed by CBD (order 2). Based on a within-subjects design and a two-tailed alpha=0.05, 36 subjects will provide 80% power to detect moderate treatment effects as small as d'=0.49. This compares favorably with the effects (d=0.7) observed by Leweke in their study comparing CBD to amisulpiride in schizophrenia patients.

SECTION VI: RESEARCH INVOLVING DRUGS, BIOLOGICS, RADIOTRACERS, PLACEBOS AND DEVICES

If this section (or one of its parts, A or B) is not applicable, state N/A and delete the rest of the section.

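### The stated 80% power at d'=0.49 fits a single 1-df within-subject comparison, not the group-by-time interaction (apparently 4 df) that the plan names as supporting the PANSS hypothesis

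*Combined protocol and SAP*

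**What the plan says.** All of the analysis text is in Section V, item 11 (Statistical Considerations).

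- **Model.** PANSS (the primary hypothesis) and CGI are analysed by linear mixed models in which "group (CBD vs. placebo) and time (see study time points) will be modeled as within-subjects factor". On the covariance, "the best fitting variance-covariance structure will be selected based on information criteria".
- **Supporting result.** "A significant group by time interaction explained by reduced symptoms over time due to CBD treatment will be supportive of our hypothesis". No other result is named as supporting the hypothesis, and the Statement of Purpose gives no time point for the PANSS reduction.
- **Power.** "Based on a within-subjects design and a two-tailed alpha=0.05, 36 subjects will provide 80% power" at d'=0.49. The next sentence sets this against an earlier trial: "This compares favorably with the effects (d=0.7) observed". The paragraph does not mention the interaction, the number of time points, a time course, a correlation, or the SD that scales d'. No other section gives a power figure.
- **Time points.** Outcome measures, item 1, schedules PANSS at Visits I-VI. Under Study Visits, screening (Visit I) happens once and the later treatment-phase visits recur in each period, from "Visit II: Baseline: Will initiate treatment with study drug following baseline assessments" to "Visit VI: (Week 4): End of treatment period visit".

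**The concern.** A power statement informs the reader only if it belongs to the test that will be used. Here the two paragraphs appear to describe different tests. A multi-df interaction spreads its sensitivity over every way the two profiles could diverge, while a 1-df contrast puts it all on one. The same sample size and the same d' can therefore give quite different power. If the interaction is what will be judged, its chance of detecting an effect of 0.49 is undocumented. If some other contrast is meant, the plan does not name it, and the choice could be made after the data are seen.

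**Working it through.** **Inputs from the documents.** n=36 in a 1:1 two-period crossover; two-sided alpha 0.05; d'=0.49; time as a factor; PANSS at baseline and weeks 1-4 of each period.

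**Inputs assumed, because the documents give none.** Compound-symmetric (CS) or AR(1) correlation of 0.3, 0.5 or 0.7 among the five CBD-minus-placebo differences; several onset shapes; no missing data.

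**Step 1: reproduce the stated figure.** For a paired comparison the noncentrality parameter is d'√n = 0.49 × 6 = 2.94. The noncentral t gives 81.6% power with 35 df and 81.5% with 34 df (one df spent on a period effect). The d' detectable with exactly 80% is 0.480. Other readings do not fit: one-sided 89.2%; parallel groups of 18 and 18, 31.2%; parallel groups of 36 and 36, 54.7%.

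**Step 2: degrees of freedom of the named test.** Two treatments by five visits gives (2−1)(5−1) = 4 df. Screening occurs once, so it cannot be crossed with treatment in both periods.

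**Step 3: same noncentrality, 4 df.** λ = 36 × 0.49² = 8.64. The noncentral F gives 57.1% with 32 denominator df (36−4, unstructured covariance) and 62.6% with 140 (35 × 4, structured).

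**Step 4: explicit time courses.** Let v be the vector of successive differences of the mean CBD-minus-placebo profile, and V its covariance for one subject. Then λ = n v′V⁻¹v. Scale d' so that 0.49 is the week-4 difference in change from baseline divided by its SD. Under CS the correlation cancels and λ = 2 n d'² Σ(s−s̄)², where s is the profile with week 4 set to 1:

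- straight line (0, .25, .5, .75, 1): 2 × 8.64 × 0.625 = 10.80
- immediate and sustained (0, 1, 1, 1, 1): 2 × 8.64 × 0.8 = 13.83

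Under AR(1) the straight line has λ of 8.66-9.16. Power of the 4-df test over all six correlation settings and both denominator df:

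| Profile (baseline, weeks 1-4) | Power at d'=0.49 |
|---|---|
| 0, .25, .5, .75, 1 | 57-74% |
| 0, .1, .5, .9, 1 | 68-86% |
| 0, .5, 1, 1, 1 | 75-85% |
| 0, 1, 1, 1, 1 | 80-98% |
| 0, .25, 1, 1, 1 | 82-91% |
| 0, 0, 1, 1, 1 | 92-98% |
| 0, 1, 1, .5, .25 (early, fading) | 80-99% |

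**Step 5: the 1-df alternatives at d'=0.49.** The week-4 change contrast, with d' on its own SD, has 81.5% by construction (Step 1, 34 df). A week-4 difference adjusted for period-specific baseline (residual SD factor √(1−ρ²), with ρ the baseline-to-week-4 correlation; 33 df) has 87-98% with d' on the change scale and 81-98% with d' on the week-4 scale. For the early, fading profile, the standardised week-4 effect on the change scale is only 0.25 × 0.49 = 0.1225; the change contrast then has 11% and the adjusted contrast 12-17%.

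**The case against.** Several points on the other side are fair.

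- **The mismatch is inferred.** The plan says only that the design is within-subjects; it does not say that a paired test was used, and it does not state 4 df. Post-baseline visits alone would give 3 df, and a linear trend 1 df. This stands, and the wording here reflects it. Still, time is called a factor, and nothing in the power paragraph makes it an interaction calculation.
- **The interaction is called supportive, not required.** This also stands. The plan allows post-hoc comparisons and uses least squares means for interpretation. But if the interaction is not the key test, no key test is named, and the need to name one is greater.
- **The cited effect of 0.7 leaves room.** With d=0.7 on the change scale, even the straight line has 90-97% power. The plan does not say how that d was scaled, so this is illustrative only. It does not turn the 80% at 0.49 into the interaction's power.
- **The low figures depend on chosen shapes and scales.** They do. The straight line is the least favourable of the six building or sustained profiles. If d' were scaled by the SD of the week-4 difference, the straight line would give 52-94% under CS and 32-43% under AR(1), but the (0, 0, 1, 1, 1) profile would give 83-99.9% and 62-89%.

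A reader might infer that the trial is underpowered, or that 36 subjects are too few. The documents do not support that: onset shape, correlation and the scale of d' are all unstated, and plausible choices put interaction power on either side of 80%. Nor is there any inflation of Type I error.

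**Conclusion.** The point holds as a mismatch between the stated power and the named test. The 80% at d'=0.49 reproduces as a 1-df within-subject comparison (81.5-81.6%). It is not the power of the group-by-time interaction, for which no figure is given. At equal noncentrality the 4-df test has 57-63%. On the change scale it ranges from 57-74% (straight line) to 68-98% (the other five building or sustained onsets). These ranges rest on the 4-df reading, the assumed correlations and complete data. This is more than a missing detail, because a reader would take the 80% as the power of the test described just before it. It should be fixed, but it does not by itself call for a change in sample size.

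**What to change.** Name one 1-df primary PANSS contrast that matches the power statement, report it with a 95% CI, and make the omnibus interaction supportive, listing baseline and weeks 1-4 as its time levels. Either form works:

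- **(a)** The CBD-minus-placebo difference in change from baseline to week 4, taken as a contrast from the planned mixed model, with baseline as a time level and period in the model. Define d' on the SD of that difference; power at 0.49 is then 81.5%.
- **(b)** The week-4 difference from a model with only post-baseline visits as responses, adjusted for period and period-specific baseline (81-98% under the assumptions above). Test the interaction in a separate model, so that baseline is not both response and covariate.

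In both cases, state which SD scales d' and the correlation assumed.

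If the sponsor prefers to keep the interaction as the key test, replace the 80% figure with its power under a stated time course, correlation and df. That also closes the gap.

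**Cost.** Wording only: no extra subjects, visits or data. The real trade-off is that a week-4 contrast would largely miss an effect that appears early and fades (about 11-17% power, against 80-99% for the interaction on the change scale). The choice should follow the time course the investigators expect, and should be made before unblinding.

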- 1. Positive and Negative Syndrome Scale (PANSS) (Visits I-VI): The PANSS includes 3 scales and 30 items: 7 items that make up the Positive Scale (eg, delusions, conceptual disorganization, hallucinatory behavior); 7 items that make up the Negative Scale (eg, blunted affect, emotional withdrawal, poor rapport, passive/apathetic social withdrawal); and 16 items that make up the General Psychopathology Scale (eg, somatic concern, anxiety, guilt feelings, mannerisms and posturing, motor retardation, uncooperativeness, disorientation, poor impulse control, preoccupation). Individual items are scored with values ranging from 1 to 7.
- 2. Personal and Social Performance Scale (PSP) (Visits I-VI): The PSP scale is a validated clinician-related scale that measures personal and social functioning in the domains of: socially useful activities (eg, work and study), personal and social relationships, self-care, disturbing and aggressive behaviors. Information from the subject and the informant will be utilized in determining the rating. The interview with the informant may be conducted by phone once the initial in-person interview has occurred and informed consent has been obtained.
- 3. Clinical Global Impression (CGI) (Visits I-VI):
 - **a.** Clinical Global Impression of Severity (CGI-S): The CGI-S consists of a single 7-point rating score of illness severity. Raters select one response based on the following question, "Considering your total clinical experience with this particular population, how mentally ill is your patient at this time?" Scores are: 1, Normal, not

- ill at all; 2, Borderline mentally ill; 3, Mildly ill; 4, Moderately ill; 5, Markedly ill; 6, Severely ill; or 7, Among the most severely ill subjects.
- b. Clinical Global Impression of Improvement (CGI-I): The CGI-I consists of a single 7-point rating score total improvement, regardless of whether or not the change it is due entirely to drug treatment. Raters select one response based on the following question, "Compared to your patient's condition at the beginning of treatment, how much has your patient changed?" Scores are: 1, Very much improved; 2, Much improved; 3, Minimally improved; 4, No change; 5, Minimally worse; 6, Much worse; or 7, Very much worse. For the CGI-I Scale, the subject's condition at the Day 1 (Baseline) visit will be the criterion for judging improvement at subsequent visits.

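### The group-by-time test of CBD carries no baseline covariate; using each period's Visit II score as a within-subject covariate could tighten the Week 4 contrast by (1-r)/2, a gain the documents do not allow to be fixed more closely than 0-50%

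*Combined protocol and SAP*

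**What the plan says.** Under General Strategy (Section V, item 11), PANSS and CGI are analysed by linear mixed models: "In these models group (CBD vs. placebo) and time (see study time points) will be modeled as within-subjects factor". The criterion is: "A significant group by time interaction explained by reduced symptoms over time due to CBD treatment will be supportive of our hypothesis". The same paragraph adds "Oder effects will also be tested" and says that "the best fitting variance-covariance structure will be selected based on information criteria". It lists no baseline covariate. It does not say whether time is categorical or linear, whether Visit II is one of its levels, or which single contrast decides the question.

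Under Study Visits, every visit except screening is repeated in each period, and the baseline visit precedes dosing: "Visit II: Baseline: Will initiate treatment with study drug following baseline assessments". The outcome list gives "Positive and Negative Syndrome Scale (PANSS) (Visits I-VI"), so each subject has a pre-dose PANSS and four weekly PANSS ratings in both periods. CGI has the same visits. Under Study Design, baseline PANSS is used to stratify the order of treatment, and the periods are separated by a washout of at least two weeks. EEG is recorded only at Visits II and VI.

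The Power Analysis states that "36 subjects will provide 80% power to detect moderate treatment effects as small as d'=0.49". It does not say which standard deviation d' is scaled by.

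**The concern.** In a crossover, stable differences between subjects already drop out of the CBD-placebo comparison. Subtracting each period's baseline as well helps only so far as that baseline predicts the outcome of the same period beyond what the subject's general level predicts. Where the prediction is weak, full subtraction brings in the noise of two further ratings.

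Stratifying the order by baseline PANSS does not deal with this, because each subject has two Visit II scores and it is their difference that enters the contrast. Nor does choosing the covariance structure by fit. In a saturated group-by-time mixed model fitted to simulated data, the Week 4 interaction coefficient equalled the difference in mean change exactly (0.000612 both ways).

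At stake is the precision of the PANSS and CGI-S contrasts in a trial fixed at 36 subjects and planned at 80% power.

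**Working it through.** **Inputs from the protocol.** N = 36 (18 per order), two-sided alpha 0.05, d' = 0.49, stated power 80%; Visit II and Weeks 1-4 rated in each period. **Not in the protocol, so assumed:** all correlations and SDs.

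**The plan's own figure.** Paired t-test, noncentrality 0.49 × √36 = 2.94. Power is 81.6% with 35 df and 81.5% with 34 df. The stated 80% reproduces.

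**Variance of the Week 4 contrast.** For one subject let dB and dY be the CBD-minus-placebo differences at Visit II and Week 4, with equal variance V and correlation r.
- Change contrast (coefficient 1): Var(dY - dB) = 2V(1-r).
- Covariate contrast (coefficient estimated, b = r): V(1-r²).
- Ratio: (1-r²)/[2(1-r)] = (1+r)/2, so the cut is (1-r)/2.

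If rw is the correlation between Visit II and Week 4 within a period and rb the correlation between ratings in different periods, then r = (rw - rb)/(1 - rb).

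**Small-sample allowance.** Estimating the coefficient inflates the adjusted variance by about 1 + 1/(36-4) = 1.031.

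| r | example rb / rw | cut, large-sample | cut, N = 36 |
|---|---|---|---|
| 0 | - | 50% | 48% |
| 0.2 | 0.5 / 0.6 | 40% | 38% |
| 0.25 | 0.6 / 0.7 | 37.5% | 36% |
| 0.5 | 0.6 / 0.8 | 25% | 23% |
| 0.6 | 0.5 / 0.8 | 20% | 17.5% |
| 0.8 | 0.5 / 0.9 | 10% | 7% |
| 0.9 | - | 5% | 2% |

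The allowance uses up the gain where (1+r)/2 × 33/32 = 1, that is at r = 64/33 - 1, about 0.94.

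**Power, if d' = 0.49 is in SDs of the change contrast.** The noncentrality becomes 2.94/√[(1+r)/2 × 1.031]. Power moves from 81.5% to 88% at r = 0.6 and to 95% at r = 0.2. In large-sample terms the variance cut equals 36/0.8 = 45 to 36/0.6 = 60 subjects analysed by change.

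**Power, if d' is instead in SDs of the Week 4 difference dY.** The change contrast has noncentrality 2.94/√[2(1-r)]: 62% power at r = 0.2 and 65% at r = 0.25, against 82% and 83% with the covariate. At r = 0.5 the change contrast has 81.5% and at r = 0.6 it has 89%, so there is no shortfall there.

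**If time is linear.** With visits at weeks 0-4, Sxx = 10. Assume constant correlation within a period and an effect that grows linearly. With SD = 1, the slope contrast scaled to Week 4 has variance 2 × 16(1-rw)/10 = 3.2(1-rw), against 4(1-rw) for the change contrast. The ratio of the covariate contrast to the slope contrast is (1+r)/1.6: 0.75, 0.78, 0.94 and 1.00 at r = 0.2, 0.25, 0.5 and 0.6. The gain is 25%, 22%, 6% and 0%, and above r = 0.6 the slope test is the more precise.

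**How the covariate enters.** In a simulation with true r = 0.4, the raw period baseline in a random-intercept model, without the subject mean, had a coefficient of about 0.84 against a within-subject value of about 0.41. With coefficient b the variance relative to the change contrast is (1 + b² - 2br)/[2(1-r)]. At b = 0.84 and r = 0.4 this is 1.034/1.2 = 0.86, a cut of 14% instead of 30%.

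**Carryover.** Suppose CBD in Period 1 leaves an effect L at the Period 2 baseline. Only one of the two orders is affected, so each mean contrast shifts by L/2.
- L persists to Week 4: the change contrast is unbiased; the adjusted one is biased by (1-b)L/2, which is 0.4L to 0.2L for b = 0.2-0.6.
- L has gone by Week 4: the bias is L/2 for change and bL/2 for adjustment, which is 0.1L to 0.3L for the same b.

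**The case against.** The strongest objection is that the benchmark is not the documented test. The plan names no Week 4 contrast and no time coding, and against a linear slope test the gain may be nil. This stands, and it is why the gain is conditional on the coding. It also means that the plan should state the coding.

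A reader might infer that 20-40% of the variance is being lost as a fact of this trial. The documents do not support that: they contain no SD or correlation, and the figure is only (1-r)/2 evaluated at r = 0.2-0.6. A higher r gives much less.

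A reader might also infer that adjustment is free. It needs no new data, but it uses one or two degrees of freedom. It can also be biased where the change contrast is not, if carryover reaches the Period 2 baseline and lasts to Week 4. The washout is at least two weeks, and the documents give no figure for carryover. If it fades by Week 4, adjustment is the less biased of the two.

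Finally, a reader might infer that the primary analysis is wrong or the trial underpowered. Neither follows. The interaction test is valid, the stated power reproduces, and d' may already be scaled to the planned contrast.

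**Conclusion.** The point holds as an efficiency improvement. With categorical time that includes Visit II, the planned Week 4 interaction fixes the baseline coefficient at 1, and a within-subject Visit II covariate would cut the variance of that contrast by (1-r)/2. The size rests on assumed correlations and on equal variances of the two within-subject differences. Under linear time the comparison is less favourable and can reach zero or reverse. Because the data are already collected and the change is one of wording, it is worth making before unblinding. It does not call the validity of the planned test into question.

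**What to change.** In Section V, item 11, before unblinding:

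1. State how time is coded, and name one primary contrast: Week 4 or the Weeks 1-4 average.
2. Model PANSS and CGI-S at Weeks 1-4 with treatment, week, treatment × week, period and a random subject effect.
3. Enter Visit II as two terms: the subject's mean of the two period baselines, and this period's deviation from that mean. The raw score alone forfeits much of the gain.
4. Use the same form for PAOFI and QLS, which are also rated at Visits II-VI. For EEG, use the same covariate with the single Visit VI outcome, since a weekly model cannot be fitted.
5. Report the change-score contrast as a sensitivity analysis, and discuss any disagreement in terms of carryover.

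The cost is SAP wording and one or two degrees of freedom, with no new visits, ratings or subjects. The price to acknowledge in the plan is the possible bias of (1-b)L/2 under persistent carryover.

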I assure the HIC that the principal investigator and all members of the research team are qualified by education, training, licensure and/or experience to assume participation in the conduct of this research trial. I also assure that the principal investigator has departmental support and sufficient resources to conduct this trial appropriately.
Chair Name (PRINT) and Signature Date
Chair Name (FRIVI) and Signature
Department
YNHH Human Subjects Protection Administrator Assurance Statement
Required when the study is conducted solely at YNHH by YNHH health care providers.
As Human Subject Protection Administrator (HSPA) for YNHH, I certify that:
I have read a copy of the protocol and approve it being conducted at YNHH.
 I agree to notify the IRB if I am aware of any real or apparent institutional conflict of interest. The principal investigator of this study is qualified to serve as P.I. and has the support of the hospital
for this research project.
YNHH HSPA Name (PRINT) and Signature Date

SECTION V: RESEARCH PLAN

1. **Statement of Purpose:** State the scientific aim(s) of the study, or the hypotheses to be tested.

This is a four week, randomized, placebo controlled, crossover trial comparing cannabidiol (CBD) to placebo in outpatients with psychotic disorder within their first five years of disease onset. We hypothesize that treatment with CBD will result in:

- a. Primary Hypotheses:
 - i. Improvement evidenced by a reduction in scores on the Positive and Negative Syndrome Scale for Schizophrenia (PANSS).
 - ii. Improvement evidenced by a reduction in the Clinical Global Impression of Severity scale (CGI).
- b. Secondary Hypothesis:
 - i. Greater improvement in functioning as measured on the "Patient Assessment of Own Functioning Inventory: (PAOFI) and the Quality of Life Scale (QLS)
 - ii. No worsening of depressive symptoms or suicidality as measured on the CDSS and CSSRS.
- c. Exploratory Hypotheses:
 - i. Exploration of the effect of CBD on EEG recordings of MMN and P300 amplitude and latency, known endophenotypes/biomarkers of Schizophrenia
- 2. **Background:** Describe the background information that led to the plan for this project. Provide references to support the expectation of obtaining useful scientific data.

There is a need to develop anti-psychotic therapeutics with novel mechanisms of action and fewer side effects:

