	Distributes the investigational device to subjects enrolled in the IRB-approved protocol:					
		SECTION VII: RECRUI	ITMENT/CONSENT AND ASSENT PROCEDURES			
Ta	Targeted Enrollment: Give the number of subjects: a. targeted for enrollment at Yale for this protocol Approximately 70 to have 36 completers b. If this is a multi-site study, give the total number of subjects targeted across all sites N/A					
Inc	Indicate recruitment methods below. Attach copies of any recruitment materials that will be used.					
	YCCI Recruitm Other (describe)	enter Newsletters ent database :	 ✓ Internet/Web Postings Mass E-mail Solicitation Departmental/Center Website Departmental/Center Research Boards ✓ Web-Based Clinical Trial Registries ✓ Clinicaltrials.gov Registry (do not send management) 	Radio Telephone Television Wewspaper aterials to HIC)		
Re	ecruitment Procedures:					

3.

1.

2.

a. Describe how potential subjects will be identified.

Potential subjects will be identified through responses to the methods of advertisements listed above. An additional document with the language used for internet/web postings has been included. Furthermore, the research team will reach out to local mental health facilities (including the Connecticut Mental Health Center, the West Haven VA and the Institute of Living) through "lunch and learns", etc. for patient referrals. A lunch and learn is a meeting that research staff schedule with clinicians and therapists at local mental health facilities where an overview of current research protocols are presented and discussed.

b. Describe how potential subjects are contacted.

Subjects will be asked to contact research staff through the advertisement methods listed above. In the event that a subject responds to an advertisement, they will be contacting study staff. In the event that subjects are referred from clinics or mental health facilities, research staff will require that the subjects' clinician contacts the subject first and then refers the subject to the research clinic.

c. Who is recruiting potential subjects?

Members of the research team.

4. Screening Procedures

- a. Will email or telephone correspondence be used to screen potential subjects for eligibility prior to the potential subject coming to the research office? ⊠Yes ☐No

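### EEG is exploratory in the hypotheses but secondary in the analysis section, and the Bonferroni family it may belong to is not defined

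*Combined protocol and SAP*

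**What the plan says.** The Statement of Purpose (Section V, item 1) has three tiers.

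- **Primary:** PANSS and CGI.
- **Secondary:** functioning on PAOFI and QLS, and absence of worsening on CDSS and CSSRS.
- **Exploratory:** "Exploration of the effect of CBD on EEG recordings of MMN and P300 amplitude and latency". EEG appears in no other tier.

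The General Strategy (Section V, item 11) sets the overall test level: "All tests will be two-sided and considered statistically significant at alpha=.05". It adds that "significance levels for secondary analyses will be adjusted for multiple tests using the Bonferroni correction". Its next paragraph says that similar mixed models will be "employed to evaluate secondary outcomes (e.g., PAOFI, EEG parameters"). It does not say which tests make up the corrected family, how many there are, or whether EEG and the clinical scales are corrected together.

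The EEG measures also differ between sections. The hypothesis names MMN and P300. The EEG testing entry under Outcome measures names P50, P300 and ASSR as the main measures, with amplitude and latency as the main dependent measures. It then adds spectral power and two coherence measures.

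**The concern.** A Bonferroni threshold is alpha divided by the number of tests, so the tier given to EEG can set the bar for the clinical secondary outcomes. If EEG is exploratory, it has no claim on the secondary error rate. If it is secondary, a literal reading puts it in the same correction as PAOFI and QLS, and each EEG parameter counted makes the functioning hypothesis harder to establish.

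Because neither the family nor the list of EEG parameters is fixed, an analyst could defend several thresholds for PAOFI and QLS and could choose among them after seeing the data.

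**Working it through.** **Inputs from the plan**

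- N = 36 in a two-period crossover ("We will recruit 36 subjects and randomly assign 18 to receive either CBD followed by placebo"). Section VII, Targeted Enrollment, confirms that 36 means completers ("Approximately 70 to have 36 completers").
- Two-sided alpha of 0.05, unadjusted: "Based on a within-subjects design and a two-tailed alpha=0.05".
- Planning effect: "36 subjects will provide 80% power to detect moderate treatment effects as small as d'=0.49". No outcome is named. The same paragraph cites d=0.7 from the earlier trial of CBD against amisulpride.
- Secondary outcomes: PAOFI and QLS (2), plus CDSS and CSSRS (2 more, if counted).

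**Assumptions, not in the plan**

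- EEG shares one Bonferroni family with the clinical secondary outcomes.
- The EEG count is 4 (MMN and P300, each by amplitude and latency, from the hypotheses) or 6 (P50, P300 and ASSR, each by amplitude and latency, from the EEG testing entry).
- A paired t test approximates the planned mixed-model comparison.
- d'=0.49 applies to PAOFI and QLS.

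**Formula.** Power = P(T > t(1 − alpha/(2m), 35)), where T is noncentral t with 35 degrees of freedom and noncentrality d × √36 = 6d, and m is the family size. At d=0.49 the noncentrality is 6 × 0.49 = 2.94.

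**Reproducing the plan's figure.** With m=1 and alpha 0.05, power is 81.6%. The effect detectable with 80% power is 0.480. The stated 80% at 0.49 is therefore reproduced.

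**Applying the correction**

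| Family | m | alpha/m | Power at d'=0.49 | Detectable d' (80%) |
|---|---|---|---|---|
| PAOFI, QLS | 2 | 0.025 | 72.3% | 0.533 |
| + CDSS, CSSRS | 4 | 0.0125 | 62.2% | 0.583 |
| PAOFI, QLS + 4 EEG | 6 | 0.00833 | 56.2% | 0.611 |
| PAOFI, QLS + 6 EEG | 8 | 0.00625 | 52.0% | 0.630 |
| PAOFI, QLS, CDSS, CSSRS + 4 EEG | 8 | 0.00625 | 52.0% | 0.630 |
| PAOFI, QLS, CDSS, CSSRS + 6 EEG | 10 | 0.005 | 48.7% | 0.645 |

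**Loss due to EEG, like for like**

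- Without CDSS and CSSRS: 72.3 − 56.2 = 16 points (4 EEG parameters) or 72.3 − 52.0 = 20 points (6).
- With CDSS and CSSRS: 62.2 − 52.0 = 10 points (4) or 62.2 − 48.7 = 14 points (6, rounded up from 13.5).
- At d=0.7, from m=2 to m=6: 96.4 − 91.1 = about 5 points.

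**Gain from Holm, two outcomes (PAOFI and QLS).** Holm rejects an outcome if its p ≤ 0.025, or if its p ≤ 0.05 and the other outcome has p ≤ 0.025. For independent outcomes at d'=0.49, power per outcome is 0.723 + (0.816 − 0.723) × 0.723 = 0.790, against 0.723 under Bonferroni. Positive correlation reduces the gain a little. Simulation gives about 78 to 79% per outcome for weak to moderate correlation.

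**The case against.** The strongest reply is that the plan never says EEG and the clinical scales share one family. The Bonferroni sentence follows a remark on post-hoc comparisons. The EEG phrase is in another paragraph, which is about the choice of model, and it is only an example. A separate correction for each domain would fit the text equally well. This stands, so the power losses above are conditional.

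Several stronger readings are tempting, and the documents do not support them.

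- **That the two sections set different thresholds for PAOFI and QLS.** Neither section gives an adjusted threshold. The hypotheses give none at all, and the General Strategy gives a rule without a count.
- **That EEG takes power from 72% to 49%.** That comparison also adds CDSS and CSSRS, which are secondary whatever happens to EEG. Bonferroni over the named secondary outcomes alone already lowers 81.6% to 72.3% or 62.2%.
- **That the trial falls short of a promised power.** No power is claimed for any secondary outcome.
- **That Bonferroni is an error.** It is valid. Holm is an improvement on it and does not correct a mistake.

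The reply does not remove the contradiction between the tiers. No other section resolves it, and the undefined family is itself the reason the threshold cannot be determined.

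**Conclusion.** The inconsistency holds. EEG has two different tiers, the Bonferroni family has no stated members or size, and the EEG measures differ between the hypotheses and the outcome list. As written, the significance threshold for the functioning hypothesis cannot be determined in advance.

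If EEG is counted in one family with the clinical outcomes, power for PAOFI or QLS at d'=0.49 falls by about 10 to 20 points, to between 49% and 56%. This rests on the shared family, the EEG count of 4 or 6, the paired t approximation, and a planning effect borrowed for outcomes it was not stated for. With a large effect the loss is small. The primary PANSS and CGI analyses are not touched. The point should be corrected, but it does not threaten the trial's main conclusion.

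**What to change.** 1. Delete EEG from the example of secondary outcomes in the General Strategy. State that EEG is exploratory and will be reported as estimates with unadjusted confidence intervals, outside the correction.
2. Name the secondary efficacy family as PAOFI and QLS (two tests). State that the hypothesis of no worsening on CDSS and CSSRS is assessed separately, as a safety hypothesis.
3. Replace Bonferroni with Holm's step-down procedure for that family. It has the same familywise error control and at least as much power: about 78 to 79% per outcome instead of 72% at d'=0.49.
4. Reconcile the EEG measures in the hypotheses (MMN, P300) with those in the EEG testing entry (P50, P300, ASSR).

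The cost is a few sentences, with no added subjects, visits or data. There are two downsides: EEG results cannot be claimed as confirmatory, and Holm does not give simple simultaneous confidence intervals. If the investigators want EEG to be confirmatory, a separate, listed EEG family would also resolve the contradiction, but the hypotheses section would then have to change to match.
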